4.1 Missing data

There will likely be participants who cannot be reached during the follow-up or decide to withdraw from the study. We plan to conduct both per-protocol (PP) analysis on participants who completed the study and intention-to-treat (ITT) analysis on all enrolled participants. The ITT analysis will be conducted only for the primary outcome, EMA-GHABP-Use, which represents HA use. For those who withdraw from the study, their EMA-GHABP-Use scores will be set to 0, indicating they would not use HAs if the outcome measures had been administered.

[figure not shown]

Figure 1. Participant timeline

REFERENCES

2. Cox RM. Using loudness data for hearing aid selection: The IHAFF approach. *The Hearing Journal*. 1995;48(2):10-39.
8. Gatehouse S. Glasgow Hearing Aid Benefit Profile: Derivation and validation of a client-centered outcome measure for hearing aid services. *Journal of the American Academy of Audiology*. 1999;10(02):80-103.

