3.6 Allocation

The treatment allocation sequence is generated using computer-generated random numbers. The assignment of treatment is based on the order of being eligible to participate in the study.

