3.8 Participant timeline

Participants for this clinical trial will be recruited through print, radio, and online advertisements, as well as mass emails/letters to established registries/lists. The principal investigators of the trial will obtain consent from participants. Following enrollment, audiologists who are blinded to the treatment assignment will administer pre-intervention assessments. Participants will then start the one-week EMA-GHABP pre-intervention measure. Seven days later, participants will return to the laboratory where audiologists, now informed of the treatment assignment, will administer the interventions. A 6-week trial will then follow. At the end of the trial, participants will return to the laboratory where research assistants, who are blinded to the treatment assignment, will administer outcome measures. Participants will then start the one-week EMA-GHABP post-intervention measure. Seven days later, participants will return to the laboratory to complete the remaining outcome measures. Participants will be debriefed and compensated for their participation. Refer to Figure 1 for the participant timeline.

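### The ITT set and its fixed non-use score take in participants who withdraw in the baseline week, before any hearing aid is fitted, which costs power in the trial's only ITT analysis

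*Combined protocol and SAP*

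**What the plan says.** Section 4.1 plans two analyses. One is a "per-protocol (PP) analysis on participants who completed the study". The other is an "intention-to-treat (ITT) analysis on all enrolled participants", limited to one outcome: "The ITT analysis will be conducted only for the primary outcome, EMA-GHABP-Use, which represents HA use". The scoring rule reads: "For those who withdraw from the study, their EMA-GHABP-Use scores will be set to 0, indicating they would not use HAs". It sets no condition on when the withdrawal happens or on whether aids were ever fitted.

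Section 3.8 gives the sequence. After consent: "Following enrollment, audiologists who are blinded to the treatment assignment will administer pre-intervention assessments". Next: "Participants will then start the one-week EMA-GHABP pre-intervention measure". Fitting comes only after that week: "Seven days later, participants will return to the laboratory where audiologists, now informed of the treatment assignment, will administer the interventions".

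Section 3.6 gives the order of assignment but no date: "The assignment of treatment is based on the order of being eligible to participate in the study".

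**The concern.** Between enrolment and fitting there is a week of smartphone surveys. Someone who finds this too much and leaves is enrolled and has withdrawn, so section 4.1 puts that person in the ITT set with the lowest possible score. No service model or technology level has been delivered at that point.

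The plan's reason for the score is that people who withdraw would not be using aids at follow-up. That is arguable for someone who tried the aids and left. It says little about the service when the person left during a baseline survey.

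The stake is precision. A few scores far below the rest shrink the expected difference between service models and widen the spread, in the only ITT analysis the trial has, on a primary outcome. Changing the score from 0 to 1, the bottom of the scale in section 3.4.1.1, softens this but does not remove it.

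**Working it through.** **Inputs from section 3.5:** difference 0.3, SD 0.53, 80 per service model, alpha 0.05/3 = 0.0167. Section 4 makes tests two-sided.

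**Inputs assumed:** completer mean 4.0 (3.5 and 4.5 also tried), and pre-fitting withdrawal rate p, equal in both groups, of 2%, 5% or 10%. The documents give no mean and no dropout rate. The t-test on one score per participant follows section 3.5 and stands in for the mixed model of section 4.

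**The plan's own figure.** Standard error = 0.53 × √(2/80) = 0.0838, and 0.3/0.0838 = 3.58. Power is 88.2% by the normal approximation and 87.6% by the noncentral t. The stated 88% reproduces.

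**With a fraction p scored at a fixed value s:**
- expected difference = 0.3 × (1 − p)
- variance = (1 − p) × 0.53² + p(1 − p) × (4.0 − s)²
- power from the noncentral t, 80 per group, alpha 0.0167

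Example, p = 5% and s = 1: difference = 0.285; variance = 0.95 × 0.2809 + 0.0475 × 9 = 0.267 + 0.428 = 0.694; SD = 0.83; power = 40%.

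| p | Difference | SD, s = 1 | Power, s = 1 | SD, s = 0 | Power, s = 0 |
|---|---|---|---|---|---|
| 0% | 0.300 | 0.53 | 88% | 0.53 | 88% |
| 2% | 0.294 | 0.67 | 64% | 0.77 | 50% |
| 5% | 0.285 | 0.83 | 40% | 1.01 | 26% |
| 10% | 0.270 | 1.03 | 23% | 1.30 | 14% |

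**Sensitivity.**
- At p = 5% and s = 1, a mean of 3.5 gives 49% and a mean of 4.5 gives 33%.
- Section 3.5 counts 240 completers, so enrolment may exceed 80 per model. With 80/(1 − p) enrolled and s = 1, power is 65%, 42% and 25%.

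**When does assignment happen?** Section 3.6 ties it to order of eligibility. In section 3.8 the baseline audiologists are blinded to an assignment, and the fitting audiologists are by then informed of one. Both suggest that it exists during the baseline week, but no date is stated. If it is made only at fitting, the enrolled set contains people with no arm, and they cannot enter a comparison of arms. The definition fails on either reading.

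**The case against.** The strongest reply is that this is ordinary ITT. Keeping assigned but untreated people in their arm protects the randomised comparison, and removing them needs a justification. The score is not false either: section 3.2.1 admits only people without hearing-aid experience, so someone who leaves before fitting is indeed a non-user. This stands, and it rules out simply deleting such participants.

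A reader might infer that quitting in the baseline week cannot depend on the arm. The documents do not support that. Section 3.7 says participants are told only about their own service, but not when. If they are told at consent, someone facing self-fitting could leave because of it, and excluding such people could bias the comparison.

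A reader might also infer that chance imbalance makes the rule biased. Four extra such withdrawals in one service model would move its mean by 4 × 3/80 = 0.15 (non-use scored 1), half the 0.3-point important difference. But that is noise already counted in the larger variance. In a simulation with equal withdrawal of 2% to 10%, the type I error was 1.5% to 1.7% against a nominal 1.67%.

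Three limits also stand. The completers-only analysis is untouched, although it drops later withdrawals too. Withdrawals after fitting inflate the variance in the same way and would remain. And the scoring rule names those who withdraw; section 4.1 states no score for those who cannot be reached.

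**Conclusion.** The point holds as one of definition and precision. As written, the ITT rule either scores people as non-users of a service that was not delivered or includes people who have no arm. It does not by itself bias the comparison.

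Under the stated assumptions, pairwise power falls from 88% to roughly 64%, 40% and 23% at 2%, 5% and 10% pre-fitting withdrawal, and to roughly 50%, 26% and 14% with the plan's score of 0. These figures show how sensitive the analysis is. They do not forecast the dropout rate, since nothing in the documents says how many participants would leave before fitting.

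**What to change.** **If assignments can still be timed.** In section 3.6, open the next assignment in the sequence at the fitting visit, once the baseline EMA week is complete, provided the single-service information in section 3.7 is not given before then. In section 4.1, define ITT as all randomised participants instead of all enrolled. Everyone randomised is still analysed, and those who leave in the baseline week never enter an arm. With 80 randomised per service model, power returns to about 88% only if nobody withdraws later.

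**If assignments were already issued at eligibility.** State that date. Keep all assigned participants in the ITT set, report pre-fitting withdrawals by arm in the flow diagram, and add a sensitivity analysis in those who attended the fitting visit. Make that set the main one only if participants did not know their service before fitting. While all assigned participants remain the main set, the lost power is not recovered, but readers can see how much the result depends on these cases. This branch may be the relevant one: section 3.3.2 dates the start of the study to 2018, and the reference list includes a 2024 publication.

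**Cost.** Wording in sections 3.6 and 4.1, one line in the flow diagram and at most one added analysis, with no extra visits or participants. Under the first option, devices must be ready for whichever arm is opened on the fitting day.

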3.4.1.2 In-situ Glasgow Hearing Aid Benefit Profile: Global score (EMA-GHABP-Global)

The EMA-GHABP-Global score is derived from the items of the in-situ GHABP that evaluate a patient's hearing disability, hearing handicap, HA benefit, and HA satisfaction across the four listening situations. This score ranges from 1 (poorer outcome) to 5 (better outcome). It will be measured for one week both pre-intervention and between 6 and 7 weeks post-intervention. During the pre-intervention assessment, only the items related to hearing disability and hearing handicap will be used.

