3.5 Sample size

The trial is designed to detect a 0.3-point difference in the primary outcome GHABP. This difference is considered a minimal important change (MIC), as participants would prefer one HA intervention over another if they had the opportunity to try both.¹⁴ Power calculations are conducted for post-hoc comparisons of the main effects, specifically the pairwise comparisons between AUD, OTC+, and OTC. Based on the MIC and an estimated standard deviation from prior research (0.53 points), a two-sample t-test would achieve 88% power to detect a difference of 0.3 points, using a conservative Bonferroni adjustment to the alpha level of 0.0167 (0.05/3), assuming 40 participants in each of the six arms, totaling 80 participants in each service model for the pairwise comparisons. Therefore, a total of 240 participants will complete the trial, with 120 participants in each study site.

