4 STATISTICAL ANALYSIS PLAN

Analyses will be conducted to determine the effect of service model, technology level, and their interaction on outcomes. For the primary outcomes, EMA-GHABP-Use and EMA-GHABP-Global, linear mixed models (LMM) will be used. LMM is selected because the primary outcomes will be collected using the EMA methodology and therefore consists of repeated observations within each participant. Linear regression models will be used for the secondary outcome dependent variables, including Retro-GHABP-Use, Retro-GHABP-Global, PHAP-Benefit, HHIE/A-Benefit, SADL, and CST-Benefit scores.

For all analyses, study site (Iowa and Tennessee) will be controlled for in the model. For both EMA-GHABP-Global and Retro-GHABP-Global, the pre-intervention GHABP scores will be controlled for in the model, with the repeated observations of pre-intervention EMA-GHABP-Global being averaged within each participant before being controlled for in the LMM. Pairwise comparisons (e.g., AUD vs. OTC+) will be conducted with an alpha level adjustment using the Tukey method. Two-tailed tests will be employed, with a significance level of .05. All statistical analyses will be performed using R statistical software.

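### EMA-GHABP-Global, the second primary outcome, is analysed only in completers, and no planned analysis tests how its service comparison depends on who stayed

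*Combined protocol and SAP*

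**What the plan says.** Section 4 names two primary outcomes with one type of model: "For the primary outcomes, EMA-GHABP-Use and EMA-GHABP-Global, linear mixed models (LMM) will be used". Section 4.1 anticipates loss: "There will likely be participants who cannot be reached during the follow-up or decide to withdraw from the study". It then plans a "per-protocol (PP) analysis on participants who completed the study" and an intention-to-treat (ITT) analysis, but restricts the latter: "The ITT analysis will be conducted only for the primary outcome, EMA-GHABP-Use, which represents HA use". The only rule for assigning a value to people who withdraw also concerns Use alone.

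For Global, section 4 says: "For both EMA-GHABP-Global and Retro-GHABP-Global, the pre-intervention GHABP scores will be controlled for in the model". The pre-intervention reports are averaged per participant and enter as a covariate, not as a response. Section 3.4.1.2 places the only post-intervention measurement in the EMA week between weeks 6 and 7, and builds the score from "hearing disability, hearing handicap, HA benefit, and HA satisfaction across the four listening situations".

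Section 3.5 counts its sample in finishers: "a total of 240 participants will complete the trial, with 120 participants in each study site". No section plans imputation, a shift analysis or any other analysis of non-completers for Global.

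**The concern.** Completion follows randomisation, and the services differ in what they offer someone who is struggling. Sections 3.3.1.1 to 3.3.1.3 give AUD participants follow-up without a stated limit, OTC+ participants at most two short visits, and OTC participants returns for limited purposes with no stated number. Leaving could therefore depend on the assigned service, though the documents do not say in which direction.

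The mixed model does not close the gap. Someone who leaves before week 6 has no post-intervention Global record, so the model has no response for that person.

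If people who would have scored low leave one service more often, the completer contrast flatters that service; the opposite pattern reverses the direction. Comparing the per-protocol and ITT results for Use would show whether withdrawal differs by service, which is part of the answer. It would not show how leavers would have scored on Global.

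**Working it through.** **Inputs from section 3.5.** MIC 0.3 points; SD 0.53 ("an estimated standard deviation from prior research (0.53 points"); 80 completers per service; alpha 0.05/3, two-sided. The SD is given for the GHABP generally; I take it to apply to Global.

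**The plan's own figure.** SE = 0.53 × √(2/80) = 0.0838. The two-sided normal approximation gives power 0.882, and the noncentral t with 158 df gives 0.876. The stated 88% reproduces. It assumes 240 completers, so the issue here is bias, not power.

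**Assumed inputs.** Leaving of 5% in one service against 15% or 20% in another; a raw completer-minus-leaver gap g of 0.265 or 0.53 points (0.5 or 1 SD); a baseline correlation r of 0.3, 0.5 or 0.7.

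**Step 1: bias before baseline adjustment.** With a proportion p leaving, the completer mean exceeds the all-randomised mean by p × g. The contrast is therefore biased by p₁g₁ − p₂g₂. With a common g:

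- 0.10 × 0.265 = 0.0265
- 0.10 × 0.53 = 0.053
- 0.15 × 0.265 = 0.0398
- 0.15 × 0.53 = 0.0795

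These are 9% to 27% of the MIC and 0.32 to 0.95 of the SE. With g = 0 the bias is 0. Equal leaving does not guarantee zero: at 15% in both services with gaps of 0.265 and 0.53, the bias is 0.15 × (0.53 − 0.265) = 0.0398.

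**Step 2: bias after the planned baseline adjustment.** I simulated 1,000,000 participants per service, with leaving logistic in the outcome and tuned to the raw gap in the higher-leaving service.

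| r | 5 v 15%, 0.5 SD | 5 v 15%, 1 SD | 5 v 20%, 0.5 SD | 5 v 20%, 1 SD | Adjusted SE |
|---|---|---|---|---|---|
| 0.3 | 0.0235 | 0.0454 | 0.0358 | 0.0712 | 0.0799 |
| 0.5 | 0.0199 | 0.0384 | 0.0302 | 0.0586 | 0.0726 |
| 0.7 | 0.0138 | 0.0275 | 0.0205 | 0.0420 | 0.0598 |

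The adjusted SE is 0.53 × √(1 − r²) × √(2/80). A hand check is the step 1 bias times (1 − r²): at r = 0.5, 0.053 × 0.75 = 0.040, against 0.0384 simulated.

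The range is 0.0138/0.3 = 5% to 0.0712/0.3 = 24% of the MIC. The largest ratio to the SE is 0.0712/0.0799 = 0.89. When leaving depended on baseline alone, the bias was 0.0016 or less, which is simulation noise.

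**Step 3: when would a conclusion change?** At r = 0.5 with three services the Tukey multiplier is 2.359, so the significance threshold is 2.359 × 0.0726 = 0.171 points. I simulated 80 completers per service from 84, 89 and 94 randomised (about 5, 10 and 15% leaving). Leavers were imputed from arm, site and baseline, and every imputed value was shifted by −0.53. The AUD against OTC decision differed from the completer decision as follows:

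| Contrast | Decisions changed |
|---|---|
| 0 | about 4% |
| 0.10 to 0.20 | 19-25% |
| 0.30 | 3-4% |

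This shift is harsher than the 0.53 gap in step 2, because it applies in full after baseline adjustment. It moved the contrast from 0.151 to 0.205, that is by 0.054, against 0.038 in step 2 for the same leaving rates. With no shift, about 1-3% of decisions changed.

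**The case against.** The restriction has a reason. Non-use can be assigned to someone who has left, whereas benefit and satisfaction are hard to define for someone no longer wearing aids. The model already adjusts for baseline Global, which removes the bias if baseline explains leaving. Withdrawal may also be low: follow-up is short, participants are compensated, and they are told there is only one arm. For early leavers, imputation without a shift adds almost nothing to the completer result, and the shift itself cannot be verified.

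All of this stands, and it keeps the point modest. It does not remove it. Difficulty in defining the score is a reason to state a target and test it. Baseline adjustment does not cover leaving that depends on how the aids worked out. The plan makes an explicit assumption about leavers for Use and none for Global.

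A reader might infer more than the documents support:

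- **That the Global result will be materially biased, or biased towards a particular service.** No rate, leaver score or direction is given, and the illustrated bias stays below one SE throughout.
- **That about one conclusion in five would change.** That figure holds only for contrasts near the threshold, under the harsher shift and with unequal leaving. With equal 10% leaving and the same shift, about 5% changed at a contrast of 0.15 and 2% at 0.30.
- **That bias could approach the whole MIC.** That needs leaver gaps of up to 2.0 points, or 2.0/0.53 = 3.8 SD, without baseline adjustment.

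**Conclusion.** The gap is certain from the text: one of two primary outcomes has a completer analysis only, and nothing in the plan shows how far its service comparison depends on who stayed. Its consequence is of unknown size. Under the assumed inputs the adjusted bias is about 0.01-0.07 points, and it is zero if leavers do not differ or baseline explains leaving. A clear null or a contrast at the MIC would rarely be overturned; a contrast near 0.17 could be. These figures rest on assumed leaving rates, gaps and correlations, and on the 0.53 SD applying to Global. The point should be fixed because it concerns a randomised comparison on a primary outcome and costs little to close. It does not show that the Global result will be wrong.

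**What to change.** Amend section 4.1 as follows.

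1. Analyse EMA-GHABP-Global by assigned arm in all randomised participants with any post-intervention EMA record, including partial weeks. Keep the completer analysis alongside. This mainly helps with people lost between weeks 6 and 7.
2. Prespecify a sensitivity analysis over all randomised participants. Impute participant-mean Global from arm, site, baseline Global and, where available, week-6 Retro-GHABP-Global. Shift the imputed values by 0, −0.265 and −0.53, stated as shifts after baseline adjustment and allowed to differ by service. Report the shift at which each service conclusion changes.
3. State the target: the Global score leavers would have reported at weeks 6-7 had they stayed in the study with their assigned aids. The negative shifts cover the case where they would have done worse.

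The cost is SAP wording and a little more analysis on data already collected. In simulation the SE of the sensitivity contrast rose by under 1% with no shift (0.0731 to 0.0733) and by about 6% at −0.53 (0.0731 to 0.0772). This tests sensitivity and does not correct the estimate: the true shift is unknown, and without a shift the analysis largely reproduces the completer result for early leavers.

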3.4 Outcomes

3.4.1 Primary outcomes

3.4.1.1 In-situ Glasgow Hearing Aid Benefit Profile: HA use (EMA-GHABP-Use)

The GHABP⁸ is a questionnaire that measures HA users' listening experience in four situations: TV listening, small conversation in quiet, conversation in noise, and group conversation. The GHABP will be administered using smartphone-based Ecological Momentary Assessment (EMA) to collect in-situ self-reports. The GHABP items evaluate HA use averaged across the four listening situations form the EMA-GHABP-Use score. The score ranges from 1 (not use HA at all) to 5 (use HA all the time). The EMA-GHABP-Use will be measured between 6- and 7-weeks post-intervention for one week.

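### The ITT rule scores withdrawn participants 0 to mean non-use, but non-use is 1 on the plan's own 1-to-5 scale

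*Combined protocol and SAP*

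**What the plan says.** Section 3.4.1.1 forms the primary outcome EMA-GHABP-Use as an average over four listening situations and anchors it: "The score ranges from 1 (not use HA at all) to 5 (use HA all the time". Section 3.4.2.1 gives the retrospective version the same anchors.

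Section 4.1 plans a per-protocol analysis of completers and an ITT analysis of everyone enrolled. It restricts the latter: "The ITT analysis will be conducted only for the primary outcome, EMA-GHABP-Use, which represents HA use". For participants who withdraw, the rule in the ITT analysis is that "their EMA-GHABP-Use scores will be set to 0, indicating they would not use HAs if the outcome measures had been administered".

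Section 3.5 supplies the yardstick: "The trial is designed to detect a 0.3-point difference in the primary outcome GHABP". It uses an SD of 0.53, 80 participants per service model and a Bonferroni alpha of 0.0167, and states 88% power. Section 4 analyses the primary outcomes with a linear mixed model because the EMA data "therefore consists of repeated observations within each participant".

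**The concern.** The plan states what the imputed value should mean, and its own scale gives that meaning the value 1. An average of items that start at 1 cannot fall below 1, so 0 is a score no observed participant could have. No section recodes the scale to start at 0, argues that withdrawal should rank below observed non-use, or plans a sensitivity analysis with another value.

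The value matters because it enters the only estimate based on all enrolled participants, and that estimate is on a primary outcome. The service models differ greatly in professional support (sections 3.3.1.1 to 3.3.1.3), so unequal withdrawal is plausible. If it occurs, part of the reported ITT contrast, read against the 0.3-point threshold, will come from a coding choice and not from hearing aid use.

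**Working it through.** **Inputs from the document.** Imputed value 0 (4.1); non-use anchor 1 (3.4.1.1); minimal important change 0.3, SD 0.53, 80 per service model, alpha 0.05/3 (3.5); two-sided tests (4).

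**Assumed inputs.** Withdrawal proportion p and completer mean m, which the document does not give; 85 enrolled per service model for the contrast/SE ratios.

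**The plan's own figure.** A two-sample test with difference 0.3, SD 0.53, 80 per group and two-sided alpha 0.0167 has power 88.2% by the normal approximation and 87.6% by the noncentral t. The stated 88% reproduces. It applies to completers and is not itself affected by this point.

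**Gap per withdrawn participant.** 1 − 0 = 1.0 point, which is 1.0/0.3 = 3.3 times the minimal important change and 1.0/0.53 = 1.9 SD.

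**Shift in a contrast.** With imputed value v, the arm mean is (1 − p)m + pv. Replacing v = 1 by v = 0 lowers it by p, so a contrast between two arms changes by (p₂ − p₁) × 1 point:

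| Withdrawal gap (percentage points) | Shift (points) | Share of 0.3 |
|---|---|---|
| 0 | 0 | 0% |
| 2 | 0.02 | 7% |
| 5 | 0.05 | 17% |
| 10 | 0.10 | 33% |

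**Direction.**
- Completers 4.0 in both groups, withdrawal 5% vs 15%. With 0: 0.95 × 4.0 − 0.85 × 4.0 = 3.80 − 3.40 = 0.40. With 1: 3.85 − 3.55 = 0.30. The 0 enlarges the contrast.
- Completers 3.8 vs 4.1, withdrawal 5% vs 10%. With 0: 3.61 − 3.69 = −0.08. With 1: 3.66 − 3.79 = −0.13. The 0 shrinks it.

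**Withdrawal gap that alone gives a 0.3 contrast**, with equal completer means: 0.3/m with 0 and 0.3/(m − 1) with 1.

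| Completer mean | Gap with 0 | Gap with 1 |
|---|---|---|
| 3.5 | 8.6 points | 12.0 points |
| 4.0 | 7.5 points | 10.0 points |
| 4.5 | 6.7 points | 8.6 points |

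**Variance.** SD = √[(1 − p) × 0.53² + p(1 − p)(m − v)²]. At m = 4.0 and p = 0.05:
- with 0: √(0.2669 + 0.0475 × 16) = 1.01
- with 1: √(0.2669 + 0.0475 × 9) = 0.83

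For completers 4.0 vs 3.7 with 5% withdrawal in both groups, the contrast is 0.95 × 0.3 = 0.285 either way. Contrast/SE is 1.88 with 0 and 2.30 with 1.

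**Power of the ITT comparison.** Noncentral t, alpha 0.05/3, n = 80/(1 − p) per group, difference 0.3(1 − p), and the mixture SD above in both groups. At m = 4.0 and p = 0.05, power is 28% with 0 and 42% with 1. Of the roughly 60 percentage points lost from 88%, about 14 are due to the 0, and about 45 come from imputing any non-use value. Over m from 3.5 to 4.5 and p from 5% to 10%, power is 12% to 34% with 0 and 19% to 52% with 1.

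**The case against.** The contradiction is hard to dispute. The case against is about weight.

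- **The bias is conditional.** With equal withdrawal the contrast does not shift, and gaps of 1 to 3 points move it by only 0.01 to 0.03. In a trial of six to seven weeks a 10-point gap may not occur. This stands, and it is why the sizes above are illustrations.
- **No worked example changes a significance call.** The Tukey critical ratio for three service models with 85 per group is about 2.36. The ratios with 0 and with 1 are 2.03 and 1.92, −0.45 and −0.90, and 1.88 and 2.30, so none crosses it. This also stands. The demonstrated harm is to the estimate, its reading against 0.3, and its precision.
- **Most of the damage is not due to the 0.** With identical completers and 5% vs 15% withdrawal, imputing 1 still gives a contrast of 0.30, and most of the power loss remains. That is correct. It is a separate criticism of single-value imputation and does not make 0 the right value. The plan also promises no power for the ITT analysis.
- **The scope is limited.** The per-protocol analysis and the other primary outcome, EMA-GHABP-Global, are untouched. True, but no other planned analysis covers all enrolled participants.

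One might read 0 as a deliberate penalty for withdrawal. Section 4.1's own explanation, that the score denotes non-use, rules this out.

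**Conclusion.** The concern holds and should be corrected before analysis. As written, the rule puts an out-of-range value into the trial's only ITT analysis and contradicts the meaning the plan gives that value. The one-point gap per withdrawn participant follows from the document alone. The consequences for contrasts, SDs and power depend on assumed withdrawal rates and completer means, and the bias in the contrast arises only if withdrawal differs between arms. The case for correction rests on the clarity of the error and its place in a primary-outcome analysis, not on any demonstrated reversal of a conclusion.

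**What to change.** In section 4.1, replace the imputed value 0 with 1, the scale's own value for non-use.

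Two clarifications belong in the same edit, since both gaps exist with either value:

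- State how an imputed score enters the mixed model. A withdrawn participant entered as a single row could carry less weight than a completer with many surveys. One participant-level score per person in the ITT analysis would avoid this.
- State how participants who cannot be reached are scored. Section 4.1 anticipates them, but its scoring rule names only those who withdraw.

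The main change costs a few words and one recoded value, with no new data. Where the arm with lower use also loses more participants, the ITT contrast will look smaller than under the present rule. Most of the ITT power loss will remain.

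### Section 4.1 scores every withdrawal as hearing-aid non-use whatever its reason or timing, so differential withdrawal can drive the ITT service-model contrast, and no sensitivity analysis tests the rule

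*Combined protocol and SAP*

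**What the plan says.** Section 4.1 (Missing data) expects two kinds of loss: "There will likely be participants who cannot be reached during the follow-up or decide to withdraw from the study". It plans a per-protocol analysis of completers and an ITT analysis of everyone enrolled, the latter for EMA-GHABP-Use only. The one scoring rule gives a 0 to those who withdraw, with the rationale "indicating they would not use HAs if the outcome measures had been administered". Nothing distinguishes withdrawals by reason or by when they occur. No score is stated for people who cannot be contacted, or for people who attend the last visits but send no EMA reports. No sensitivity analysis of the rule is planned.

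Three other places bear on this:

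- Section 3.4.1.1 defines the score from 1 to 5, with 1 already meaning no use.
- Section 3.8 places enrolment and a one-week baseline EMA before fitting, and the post-intervention EMA week after the six-week visit. Section 3.4.2.1 collects Retro-GHABP-Use at week 6.
- Sections 3.3.1.1 to 3.3.1.3 give the arms different contact: unlimited follow-up in AUD, at most two 15-minute visits in OTC+, and returns only for preset reselection or device problems in OTC.

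**The concern.** The rule equates leaving the study with rejecting the devices. The trial's own timeline shows two groups for whom this is wrong or contradicted by data. A participant who leaves during the baseline EMA week has never had a hearing aid to reject. A participant who reports regular use on Retro-GHABP-Use at week 6 and then leaves during the EMA week is scored as a non-user against a value the trial already holds. Someone who leaves because of illness, relocation or the burden of the EMA weeks is treated in the same way.

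In a two-sided comparison of service models, this moves the contrast against whichever model loses more people. Contact differs by design, so unequal retention is plausible. What is at stake is the interpretation of the only ITT result in the plan: a service difference in use could appear when use among those measured is the same.

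**Working it through.** **Inputs from the documents.** Section 3.5: difference 0.3; "an estimated standard deviation from prior research (0.53 points"); 80 per service model; alpha 0.0167 per pair. Section 4: "Two-tailed tests will be employed, with a significance level of .05", with Tukey adjustment for pairwise comparisons. Section 3.4.1.1: scale 1 to 5.

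**Assumptions (not in the documents).** Completer mean m of 3, 4 or 4.5; withdrawal rates as shown; withdrawal unrelated to use.

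**Step 1: the plan's own figure.** Section 3.5 states that "a two-sample t-test would achieve 88% power to detect a difference of 0.3 points". With 80 per group, the noncentrality is (0.3/0.53) × √(80/2) = 3.58. At two-sided 0.0167, power is 88.2% (normal) or 87.6% (t). The figure reproduces. It uses SD 0.53 and makes no allowance for the ITT rule.

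**Step 2: shift caused by a withdrawal gap.** If completers have the same mean in both groups,

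shift = (difference in withdrawal proportion) × (m − assigned score).

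Setting the shift to 0.3 gives a gap of 0.3/(m − score):

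| m | score 0 | score 1 |
|---|---|---|
| 3 | 0.3/3 = 10.0 points | 0.3/2 = 15.0 points |
| 4 | 0.3/4 = 7.5 points | 0.3/3 = 10.0 points |
| 4.5 | 0.3/4.5 = 6.7 points | 0.3/3.5 = 8.6 points |

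On 80 per service model, the score-0 gaps are 8, 6 and about 5 people. The problem remains when non-use is scored at the scale's own value of 1, so it is separate from 0 lying below the scale.

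**Step 3: how often a difference is declared.** Simulation with identical completers, N(m, 0.53), in all three service models; one score per participant; Tukey at .05; 80 or 89 per model (89 is 80/0.90, the enrolment needed for 80 completers at 10% loss); m of 3 to 4.5; score 0 or 1.

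| Withdrawal in the three models | At least one pair significant |
|---|---|
| 5/5/15% | roughly 38 to 60% |
| 5/5/10% | roughly 13 to 21% |
| equal (5% or 10% in all) | about 5% |

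For a single pair at alpha 0.0167 with 80 per group and score 0, 5% against 15% rejects in about 29 to 33% of runs, 5% against 10% in about 8 to 9%, and 10% against 10% in 1.5 to 1.8%. These rates are lower because they count one pair at a stricter level.

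**Step 4: equal withdrawal.** At rate p in both groups, a true completer difference is multiplied by (1 − p), and the SD becomes √[(1 − p) × 0.53² + p(1 − p)(m − score)²]. With m = 4 and score 0:

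- p = 5%: SD = √(0.267 + 0.760) = 1.01, contrast 0.95 × 0.3 = 0.285, power about 28%.
- p = 10%: SD = √(0.253 + 1.440) = 1.30, contrast 0.90 × 0.3 = 0.27, power about 15%.

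Both powers allow for enrolling 80/(1 − p) per group. There is no bias, only shrinkage and noise.

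**The case against.** Four points can fairly be made for the plan.

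1. *Counting dropout as non-use is a recognised composite strategy, and the plan states its rationale.* This stands for people who left because they gave up the devices. It does not cover those who left before fitting or who had just reported use.

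2. *The size is conditional.* The documents give no withdrawal rate, no gap between service models, no reasons and no expected mean use. Losses unrelated to the devices should tend to balance under randomisation, and a threefold gap might itself be an effect of the service model. The simulation also uses one score per participant, whereas the planned model uses repeated EMA records, and the plan does not say how many records a withdrawn participant contributes. All of this stands. A reader might infer that the ITT contrast reflects departures more than hearing-aid use; the documents do not support that as a fact.

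3. *The per-protocol analysis would expose the problem.* In part. No difference among completers beside an ITT difference would point to withdrawal as the driver. But the per-protocol analysis omits everyone who left, so it cannot show which of them were non-users or how far the conclusion depends on the assigned score.

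4. *Unreachable participants are probably meant to count as withdrawn.* A reader might infer that they fall out of the ITT analysis. Since section 4.1 commits to everyone enrolled, treating them as withdrawn fits that commitment better. This is an ambiguity that one sentence settles, and it does not show that the ITT set is incomplete.

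**Conclusion.** The concern holds as a conditional one and should be addressed. The rule ignores reason and timing, conflicts with data the trial will hold for some participants, and has no sensitivity analysis beyond the completer-only one. Differential withdrawal alone can therefore produce a service-model difference as large as the 0.3-point design difference. That takes a gap of about 7 to 10 points with score 0, or 9 to 15 points with score 1, for completer means of 4.5 to 3. At an assumed 5/5/15%, a false service difference in use among those measured would be declared in roughly 38 to 60% of trials.

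These figures assume identical use among completers, withdrawal unrelated to use, SD 0.53 and one score per participant. If withdrawal is equal, or is truly device rejection, the spurious contrast disappears.

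**What to change.** - **Record exit reason and timing** (before or after fitting, before or after the week-6 visit), with reasons classed by someone blind to arm.
- **Score as non-use only those who stopped wearing, returned or rejected the devices**, at the scale's own no-use value. State how such a participant enters the mixed model of repeated records.
- **For all other missing EMA-GHABP-Use** (unrelated reasons, unreachable or reason unknown, attended but no EMA reports), state that the participants are in the ITT analysis. Use multiple imputation that draws on Retro-GHABP-Use where recorded.
- **Keep the rule that scores every withdrawal as non-use as a sensitivity analysis.**
- **Add a tipping-point table by service model**, moving the assumed score from non-use to the completer mean. Early leavers have no week-6 value, and EMA-GHABP-Use has no baseline, so imputation within arm would largely return the completer mean on an untestable assumption. For them the table must carry the weight.

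The cost is SAP wording, one exit-reason item on the form, some judgement in classing reasons and a little more analysis. Unreachable participants can give no reason, which is why they belong with the imputed group. If data collection has ended, the imputation and tipping-point analyses still need only SAP wording.
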